## Supporting Evidence

### *Pre-clinical studies:*

In the 21st century, there were two other epidemics with coronaviruses that were associated with high mortality, SARS in 2003 and MERS in 2012. In a mouse model of SARS infection, animals receiving immune serum from infected mice were protected against lower airway disease after intranasal challenge with virus. Several groups have also identified monoclonal neutralizing antibodies that have shown efficacy in animal models of SARS. In a mouse model of MERS infection, transfusion of sera from MERS-infected camels was efficacious for both prophylaxis and treatment. Similar results for convalescent sera were obtained in a marmoset model of MERS.

### *Clinical studies:*

In both SARS and MERS outbreaks, the high mortality and absence of effective therapies led to the use of convalescent plasma in human studies. The largest study involved the treatment of 80 patients in Hong Kong with SARS. Patients treated before day 14 had improved prognosis defined by discharge from hospital before day 22, consistent with the notion that earlier administration is more likely to be effective. In addition, those who were RT-PCR positive and seronegative for coronavirus at the time of therapy had improved prognosis. There is also some anecdotal information on the use of convalescent plasma in seriously ill individuals. Three patients with SARS in Taiwan were treated with 500 ml of convalescent plasma, resulting in a reduction in plasma virus titer and each survived. Three patients with MERS in South Korea were treated with convalescent plasma, but only two of the recipients had neutralizing antibody in their plasma. The latter study highlights a challenge in using convalescent plasma, namely, that some who recover from viral disease may not have high titers of neutralizing antibody. Consistent with this point, an analysis of 99 samples of convalescent sera from patients with MERS showed that 87 had neutralizing antibody with a geometric mean titer of 1:61. This suggests that antibodies decline with time and/or that only some patients make high titer responses. It is also possible that other types of non-neutralizing antibodies are made that contribute to protection and recovery as described for other viral diseases.

## Current Trials of CP in Severe COVID-19

There are also recent reports of improvement from SARS-CoV-2 infection in hospitalized patients given convalescent plasma ([http://www.xinhuanet.com/english/2020-02/28/c\\_138828177.htm](http://www.xinhuanet.com/english/2020-02/28/c_138828177.htm)). In another report, 5 critically ill patients with COVID-19 were given high-titer convalescent plasma. All patients had improved viral loads, 4 had resolution of ARDS, and 3 were weaned from mechanical ventilation within 2 weeks of treatment. There were no reported adverse events in the treated patients. However, this study was uncontrolled and all 5 patients also received other anti-viral treatments and corticosteroids, highlighting the need for a randomized controlled trial. In another case series, 10 patients with severe COVID-19 were administered convalescent plasma, and all improved clinically without any serious adverse events. In a historical control group matched to the 10 treated patients, only 1 out of 10 patients showed similar improvements.

## 2.3 Risk/Benefit Assessment

### 2.3.1 Known potential risks

A theoretical risk of CP is antibody-dependent enhancement (ADE) of illness. ADE involves an enhancement of disease in the presence of cross-reacting antibodies that activate receptors that suppress immune response. For coronaviruses, there is the theoretical concern that antibodies to one type of coronavirus could enhance infection to another viral strain. However, use of CP in the COVID-19 epidemic will rely on products with neutralizing antibody against the same virus, SARS-CoV-2, which should make ADE unlikely. The available evidence from the use of CP in patients with SARS1 and MERS and anecdotal evidence of its use in patients with COVID-19 ([http://www.xinhuanet.com/english/2020-02/28/c\\_138828177.htm](http://www.xinhuanet.com/english/2020-02/28/c_138828177.htm)) and, suggest it is safe. Nevertheless, this trial will monitor illness severity over time for any evidence of enhanced infection.

Another theoretical risk is that antibody administration to those exposed to SARS-CoV-2 may avoid disease but modify the immune response such that those individuals mount attenuated immune responses, which would leave them vulnerable to subsequent re-infection. In this regard, passive antibody administration before vaccination with respiratory syncytial virus was reported to attenuate humoral but not cellular immunity. This concern could be investigated as part of a clinical trial by measuring immune responses in those exposed and treated with convalescent plasma to prevent disease. If the concern proved real, these individuals could be vaccinated against COVID-19 when a vaccine becomes available. *These concerns seem modest compared to the possibility of limiting the duration and severity of disease, and avoiding interventions like mechanical ventilation, ARDS and sepsis.*

Finally, there are risks associated with any transfusion of plasma including transmission of transfusion transmitted viruses (e.g. HIV, HBV, HCV, etc.), allergic transfusion reactions, anaphylaxis to transfusion, febrile transfusion reaction, transfusion related acute lung injury (TRALI), transfusion associated cardiac overload (TACO), and hemolysis should ABO incompatible plasma be administered. In addition, donors will fulfill donor requirements for whole blood donation and frequent apheresis plasma donation with the exception of recent illness, in this case COVID-19 infection. With current practice, transfusion transmission of infections is very rare. In addition, the risk of TRALI is also very rare because CP will be collected from populations with reduced risk for allo-antibodies such as: males, never pregnant females, and females who test negative for HLA antibodies.

Preliminary safety results from the Expanded Access Program for CP in moderate-severe COVID-19 have been posted, but not yet peer-reviewed (<https://www.medrxiv.org/content/10.1101/2020.05.12.20099879v1>). Among 5000 transfusions, there were 36 serious adverse events (0.7%) with 25 adjudicated as related (0.5%). Related

events included mortality (n=4, 0.08%), TACO (n=11, 0.22%), TRALI (n=7, 0.14%) and allergic reaction (n=3, 0.06%). Another 11 deaths were reported but judged not to be related.

### 2.3.2 Known potential benefits

A key potential benefit is treatment for established infection. Convalescent plasma would be administered to those with clinical disease in an effort to reduce their symptoms and mortality. Based on the historical experience with antibody administration, it can be anticipated that *antibody administration relatively early in the course of disease would be more effective in preventing disease progression than in the treatment of established severe disease.*

Given that historical and current anecdotal data on use of CP suggest it is safe in coronavirus infection, the high mortality of COVID-19, particularly in elderly and vulnerable persons, suggests that the benefits of its use in those at high risk for or with early disease outweigh the risks. However, for all cases where convalescent plasma administration is considered, a risk-benefit assessment must be conducted to assess individual variables.

## 3. Objectives and Endpoints

Objectives	Endpoints	Justification for endpoints
Primary		
To establish the efficacy of a single dose of convalescent plasma (CP) for preventing the progression from mild to severe COVID-19 illness.	Disease progression defined as death or hospital admission or seeking emergency or urgent care within 15 days of randomization	This will allow quantification of disease progression from mild to moderate/severe/critical
Secondary and Exploratory		
Determine the effect of CP on COVID-19 illness severity	Worst severity rating on the WHO's COVID Ordinal Scale for Clinical Improvement during the 30 days following randomization 
 
○ Death
 
○ Hospitalized, intubated, mechanically ventilated and requiring additional organ support (pressors, renal replacement therapy)
 
○ Hospitalized on invasive mechanical ventilation or ECMO
 
○ Hospitalized on non-invasive ventilation or high flow nasal cannula
 
○ Hospitalized on supplemental oxygen
 
	This scale was developed by a special World Health Organization (WHO) committee for quantifying COVID-19 illness severity

	
 
○ Hospitalized not on supplemental oxygen
 
○ Not hospitalized with limitation in activity (continued symptoms)
 
○ Not hospitalized without limitation in activity (no symptoms)
 
	
Determine the effect of CP on COVID-19 illness severity	
Time to disease progression on the COVID Outpatient Ordinal Outcome Scale censored at 15 days after randomization
 
 
● Patient requires care in the hospital
 
● Patient requires care in the ED or urgent care
 
● Patient at home with symptoms rated as moderate (defined as fever, shortness of breath, abdominal pain)
 
● Patient at home with symptoms rated as mild (defined as afebrile, constitutional symptoms (flu-like illness) without shortness of breath)
 
● Patient in their usual state of health
 
	
This scale was adapted for outpatient use from Harrell 2020 (http://hbiostat.org/proj/covid19/bayesplan.html) to provide more granular detail for outpatients than the WHO scale.

Determine the effect of CP on prevention of hospitalization	Hospital-free days during the 30 days following randomization	This is a more graded measurement of hospitalization than the binary primary outcome
Determine the effect of CP on mortality	All-cause mortality at 30 days	Critical safety outcome
Determine the effect of CP on the duration of symptoms	Symptom inventory measured using the CDC list of COVID-19 symptoms on days 2, 4, 6, 8, 10, 14, 15, 30	Patient centered outcome relevant to patient experience of illness
Characterize the immunological response to CP administration	Neutralizing antibody titers at days 0 (pre-intervention and post-intervention), 15, and 30 using different methods	Determine if CP administration increases recipient antibody titers that can inhibit virus

Measure change in spike protein IgG titers in CP recipient from pre- to post-CP	Spike protein IgG antibody titers pre and post CP administration using different methods	Determine distribution of CP antibodies into recipient
---	--	--

### 3.1 Primary Endpoint

*Operational definition of Hospitalization Care in the primary endpoint:*

- The endpoint is determined based on the order to admit the patient to an inpatient hospital bed (including admission to observation status). Patients may board in emergency departments or other outpatient areas awaiting inpatient beds for some time; therefore, the intent to place the patient in an inpatient bed is considered to be hospitalization. Observation in an emergency department observation unit would not count as hospitalization but only as emergency care. In the event that a patient worsens in the emergency department shortly after administration of the intervention and requires admission during that same visit, we will consider that that patient has met this primary endpoint.

*Operational definition of Emergency Care in the primary endpoint:*

- This endpoint is determined based on any presentation to an emergency department or urgent clinic for care. COVID-19 patients may be redirected to special areas adjacent to or outside of the usual emergency department for evaluation and treatment; therefore, the presentation for emergency or urgent care is considered the endpoint rather than physical entry into a specific area.

*Operational definition of Death in the primary endpoint:*

- Patients who die outside the hospital during the 15 days following randomization will meet this endpoint. Death notice or public records can confirm death.

*Justification of the primary endpoint:*

Hospitalization is a hard metric of meaningful worsening of disease.

- Hospitalization is a readily observable and objective outcome. It does not depend on self assessment, does not depend on return to the enrollment site, and can be verified by self-report, proxy-report, or even limited source documents from any admitting hospital or clinic. As such, it has low vulnerability to missing data or bias.
- The endpoint is a marker for worsening of disease. Hospitalization is a marker for the need of more intensive treatment that cannot be managed as an outpatient and is similar to the criteria used to characterize an adverse event as serious.
- The endpoint matters to patients. The need for hospitalization is a significant and meaningful event for patients. Hospitalization also removes patients from families and support systems further aggravating other symptoms of disease progression.
- The endpoint matters to the healthcare system. The need for hospitalization is the primary indicator of demand and capacity of the healthcare and public health systems during pandemic illness. This endpoint has direct implications for healthcare utilization in times of healthcare system stress.
- Preventing treatment imbalances within site (while maintaining randomness in treatment assignment) minimizes the effect of variations in practice or hospital capacity on the primary endpoint.

- Fifteen days is an appropriate time frame given the natural history of COVID-19.  
The median time to hospitalization from symptom onset is approximately 9-10 days. Longer time periods increase the risk of competing unrelated events.

Seeking Emergency Care is a hard metric of meaningful worsening of disease.

- Emergency and Urgent care is readily observable and objective. Like hospitalization, this event can be captured with limited source documents or patient report, and thus has low vulnerability to missing data or bias.
- Seeking medical care represents symptom progression that a patient cannot manage at home. Therefore, this is an event of sufficient severity to require action.
- The endpoint matters to the healthcare system. Emergency and urgent care represents health care utilization.
- This endpoint captures moderate disease progression. Patients treated in emergency departments or clinics but not admitted to the hospital have actionable disease progression that is less severe than those admitted to the hospital.

Death is the most profound worsening of disease

- Subject death is readily ascertained and objective. Death can be confirmed by multiple data sources.

### **3.2 Secondary Endpoints**

These endpoints explore the trajectory of illness in greater detail. These will provide additional information about CP effects on disease progression and maximal disease severity.

- WHO's COVID Ordinal Scale for Clinical Improvement
- COVID-19 Outpatient Ordinal Scale
- Hospital-free days
- All-cause mortality

### **3.3 Exploratory Endpoints**

- Symptom inventory

These endpoints will determine the ability of CP to increase the titers of neutralizing antibodies in recipients.

- Antibody titers at pre-infusion, post-infusion and at 15 and 30 days in CP recipients and controls
- Spike protein IgG antibody titers pre and post CP administration

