### 1.5 Study Flow and Daily Data Collection

The enrollment and follow-up process will be tailored to the particulars of each site, but will generally be as follows.

- Units of SARS-CoV-2 convalescent plasma (CP) with neutralizing SARS-CoV2 antibodies titers of  $\geq 1:160$  will be sent to sites for storage.
- Site study teams will be notified whenever a COVID-19 test is ordered on an Emergency Department patient.
- The site study team will then consult with the treating team and/or the electronic health record to screen for potential eligibility.
- If the treating team anticipates discharge, the site study team will connect with the patient on the patient's mobile device, by bedside telephone in the ED room, on a study provided tablet device, or in person using all appropriate personal protective equipment. They will verbally describe the trial and participation and complete the informed consent process.
- Those wishing to participate will complete the electronic informed consent document and provide contact information.
- When all eligibility criteria have been met, the site study team will enroll and randomize the subject in the study web-based clinical trial management system (WebDCU).
- The site study team will complete Day 0 (Baseline) case report forms.
- All subjects will have a pre-infusion blood draw. Blood from consented subjects will be sent for blood type. Blood from all subjects will be processed and frozen for later analysis.
- Residual viral media samples from nasopharyngeal swabs and/or saliva samples will also be collected during the enrollment visit.**
- If randomized to CP, an order will be placed by the study team to the blood bank for 1 unit of study CP.
- If randomized to placebo, an order will be placed to the pharmacy for 250 ml NS + 1-5 ml parenteral MVI (see [MOP](#) for details).
- CP or placebo will then be infused in a fashion blinded to the participant over 30 minutes (or longer depending on subject's cardiopulmonary status) with the infusion bag covered.
- The participant will be observed in the emergency department for at least 1 hour after infusion. At one hour, another blood sample will be drawn and frozen for later analysis.
- The participant will then be discharged from the emergency department.
- The central study team follow-up core will contact the participant by telephone or video

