- Assessment of S1 titers in CP recipients and controls pre-CP, 1 hr post, 15 and 30 days post to assess the impact of CP and determine whether titers rise with time (showing endogenous response not negatively impacted by CP)
- Use Lentiviral pseudovirus reporter assay to quantitate neutralization Ab titers in recipients of CP units at pre- post-CP.
- Neutralization of SARS CoV-2 Plaque Formation (gold standard) in a subset of CP to correlate with other assays.

In addition to the blood samples collection outlined above, for subjects who consent to participating in an optional study evaluating the evolution of the adaptive immune response in CP recipients, an additional 20 ml of whole blood will be collected on the day of enrollment and

on study days 15 and 30. These samples will be shipped within 1 day of collection to a central laboratory for processing.

Residual viral media and saliva specimens collected will be analyzed for SARS-CoV-2 viral genotype

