### **8.1.4 Blood Sample Storage, Processing and Shipping for Antibody Titer Testing**

Each site will ship the 4 blood samples from each participant to the central testing laboratory (University of Pittsburgh). The site can ship all of the samples for one participant together in a single package. Labels for samples with barcodes will be provided to sites in advance in order to ensure accurate sample tracking. Labeling samples with the subject ID from WebDCU can serve as a backup procedure.

*Antibody titres:* To determine the immunologic response to CP administration, we will measure anti-SARS-CoV-2 IgG, IgM and neutralizing antibody titres pre-intervention, post-intervention and at days 15 and 30.

Testing will be identical to the testing performed to determine the titer of the donor CP. We will determine the IgG/IgM titers to SARS CoV-2 S (Spike) protein using enzyme linked immunoassays (BSL-2+). There are multiple assays available and in development. We will compare titres from the Vitalant (Ortho VITROS Anti-SARS-CoV2 Total) assay to titres from other assays (e.g. Euroimmun ELISA) whenever possible to determine the concordance. In a subset of these samples, we will measure antibody neutralization titers using the gold standard assay, a viral plaque assay performed in a BSL-3 facility at University of Pittsburgh. This will allow us to determine whether high titers in binding assays actually represent superior neutralization capacity for inhibiting SARS-CoV-2 infection.

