#### **9.2.4 Analysis of Secondary and Exploratory Outcomes**

This study is designed to test the primary hypothesis; however, it also offers the opportunity to evaluate important additional secondary and exploratory outcomes. Continuous secondary endpoints will be summarized by the mean and standard deviation with corresponding 95% confidence intervals. Categorical endpoints will be summarized by the sample proportions with exact or asymptotic confidence intervals. For time to event analyses, we will construct Kaplan Meier curves. Our analyses will consider sex as a biological variable that may affect treatment outcomes for COVID-19.

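### No baseline-adjusted between-arm estimate is named for post-infusion, Day 15 or Day 30 antibody titers, although a pre-infusion sample is planned for every participant

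*Combined protocol and SAP*

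**What the plan says.** Section 3 lists the endpoint as "Neutralizing antibody titers at days 0 (pre-intervention and post-intervention), 15, and 30 using different methods". Section 3.3 covers both arms, "Antibody titers at pre-infusion, post-infusion and at 15 and 30 days in CP recipients and controls", and gives the purpose: "These endpoints will determine the ability of CP to increase the titers of neutralizing antibodies in recipients".

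The baseline sample is planned for everyone. Section 1.5 states: "All subjects will have a pre-infusion blood draw". Section 8.1.4 adds that "we will measure anti-SARS-CoV-2 IgG, IgM and neutralizing antibody titres pre-intervention, post-intervention and at days 15 and 30".

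For analysis, Section 9.2.4 offers one general sentence: "Continuous secondary endpoints will be summarized by the mean and standard deviation with corresponding 95% confidence intervals". It names no between-arm model, covariate or scale for titers. Read literally it covers secondary endpoints only. Sections 1.2 and 3.3 class titers as exploratory, while Section 1.1 and the heading of 8.1.3 class them as secondary.

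Baseline antibody is used in three other places:
- The Section 3 table includes a pre-to-post change in spike IgG, in CP recipients only.
- An S1 bullet in Section 8.1.3 follows both arms from before infusion to Day 30, to see whether titers rise. It names no estimator.
- Section 9.2.1 examines pre-treatment antibody as a modifier of the CP effect on outcome.

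Assay coverage is worded inconsistently. Section 8.1.3 says: "Use Lentiviral pseudovirus reporter assay to quantitate neutralization Ab titers in recipients of CP units at pre- post-CP". That is one arm and two times. Section 3.3 gives both arms and four times, and Section 8.1.4 gives four times. For the plaque assay, Section 8.1.4 says: "In a subset of these samples, we will measure antibody neutralization titers using the gold standard assay".

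**The concern.** Characterizing the immunologic response is the only secondary objective in Sections 1.1 and 1.2. It contains two between-arm questions. One is whether plasma raises recipient titers soon after infusion. The other is whether it blunts the recipient's own response later, a risk raised in Section 2.3.1. Section 8.1.3 hopes to show that the endogenous response is not harmed. An imprecise comparison showing no difference is weak support for that, and is easily misread as evidence of no blunting.

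Participants may enter up to 7 days after symptom onset, so some probably already have antibody and others none. To the extent that this spread persists in later samples, it inflates the variance of a comparison of arm means that leaves the baseline out. Adjusting for the pre-infusion titer removes that part. With no method named, the analyst must choose after the fact, and one common choice, the simple change score, can be worse than no adjustment.

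**Working it through.** The documents state no sample size, SD, effect size or power for any titer endpoint, so there is no plan figure to reproduce.

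**Inputs from the documents:** 1:1 allocation (Section 6.3); maximum 450 per arm (Section 1.2); pre-infusion draw for all subjects (Section 1.5).

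**Assumed input:** r, the correlation between pre-infusion and later log titer, taken from 0 to 0.9. All 450 per arm are assumed sampled, which is a best case.

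**Formulas**, as large-sample variance of the between-arm difference relative to comparing follow-up means alone:
- ANCOVA: 1 - r². The equivalent gain in sample size is 1/(1 - r²).
- Change score: 2(1 - r).
- 95% half-width under ANCOVA, in SD units: 1.96 × √(2/450) × √(1 - r²). At r = 0 this is 1.96 × 0.0667 = 0.131.

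| r | ANCOVA variance ratio | Equivalent n | Change-score variance ratio | ANCOVA half-width (SD) |
|---|---|---|---|---|
| 0 | 1.00 | ×1.00 | 2.00 | 0.131 |
| 0.3 | 0.91 | ×1.10 | 1.40 | 0.125 |
| 0.5 | 0.75 | ×1.33 | 1.00 | 0.113 |
| 0.7 | 0.51 | ×1.96 | 0.60 | 0.093 |
| 0.9 | 0.19 | ×5.26 | 0.20 | 0.057 |

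At this sample size adjustment costs essentially nothing even when r = 0. A change score loses precision whenever r is below 0.5.

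**Illustration for Day 30, all inputs assumed:** 400 sampled per arm, SD of 2 log2 units, two-sided 5%, and a geometric mean titer 25% lower after CP. The effect is log2(1/0.75) = 0.415.
- r = 0: SE = 2 × √(2/400) = 0.141, power 0.835.
- r = 0.3: SE = 0.141 × √0.91 = 0.135, power 0.868.
- r = 0.5: SE = 0.141 × √0.75 = 0.122, power 0.923.

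The formulas assume one r and equal variances in both arms. That is least safe soon after infusion. Section 6.2 admits units labelled from 1:160 to above 1:10240, which adds variation in the CP arm unrelated to the recipient's baseline. This is why the fix asks for robust standard errors.

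**The case against.** A reader might infer that the plan has decided to summarize titers by arm and leave the pre-infusion value out. The documents do not say that. Section 9.2.4 is a generic sentence that neither mentions arms for titers nor excludes a baseline. Section 3.3 lists the pre-infusion titer within the endpoint, and the S1 bullet in Section 8.1.3 is a two-arm course that starts before infusion. This is silence on the estimator, and the point is confined to that.

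A reader might also infer a very large gain at 1 hour. With the assumed 400 per arm and SD of 2 log2 units, power for a 10% higher titer would go from 16% unadjusted to 61% at r = 0.9. The documents do not support resting on this. Nothing makes a 10% difference meaningful, and the labels in Section 6.2 move in fourfold steps. A correlation that high is doubtful when donor units vary so widely. On the same assumptions a 50% higher titer already has about 98.5% power unadjusted: log2(1.5) = 0.585, 0.585/0.1414 = 4.14, and 4.14 - 1.96 = 2.18.

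Two further objections stand. No test, alpha or success criterion is attached to titers, so no trial decision changes. And Section 1.5 promises a blood draw, not a neutralizing titer by one common assay; if the narrow wording in Section 8.1.3 governs, extending that assay would be new laboratory work.

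None of this supplies the missing estimator. The spike IgG change has no control arm, and the S1 bullet gives no estimate to compute.

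**Conclusion.** The point holds as a minor one. The plan collects the baseline and asks between-arm questions about later titers, but names no baseline-adjusted estimate to answer them. ANCOVA would reduce the variance by 9% at r = 0.3 and 25% at r = 0.5, and would leave it unchanged at r = 0. The size rests wholly on r, which the documents do not give. It may be low at Days 15 and 30 if endogenous antibody develops in between, so the gain there may be modest. The assay-coverage wording is a separate inconsistency and does not affect this conclusion.

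**What to change.** In Section 9.2.4, state that post-infusion, Day 15 and Day 30 log titers measured by a common assay are compared between arms by ANCOVA. The covariates are the pre-infusion log titer and an indicator for a pre-infusion value below detection. Use robust standard errors, because variation in donor titer can make the CP arm more variable. Report the ratio of geometric means with a 95% interval at each time. Make clear that this applies to titers whether they are classed as secondary or exploratory.

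The cost is wording only, applied to samples and assays already planned; it needs no new visit or draw.

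Separately, reconcile the pseudovirus neutralization bullet in Section 8.1.3 with Sections 3.3 and 8.1.4, so that the arms and times to be assayed are stated once. Extending any assay beyond what is already planned is not part of this fix, and its cost would have to be judged on its own.
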